## **STUDY PROCEDURES AND SCHEDULE**

This is an open-label clinical trial treating 26 adult patients with chronic delta hepatitis with lonafarnib plus ritonavir and lambda interferon for 24 weeks. Patients will undergo baseline testing including blood draws, imaging, safety consults, and liver biopsy with portal pressure measurements prior to starting therapy. During therapy, all patients will be monitored with quantitative HDV RNA and HBV DNA levels as well as routine safety measures and liver function tests. After 24 weeks, therapy will be stopped and patients will again undergo repeated testing including blood draws, imaging, and safety consults. After stopping therapy, patients will be followed for an additional 24 weeks. At the end of the 24 weeks of post-therapy follow-up, patients will be re-admitted to the NIH Clinical Center and will undergo repeat testing including blood draws, imaging, as well as a transjugular liver biopsy with hepatic venous pressure gradient measurements.

## **STUDY ENTRY CRITERIA**

### ***Inclusion Criteria:***

1. Age 18 years or above, male or female.
2. Presence of anti-HDV in serum.
3. Presence of quantifiable HDV RNA in serum at three time pre-treatment points with a mean HDV RNA level  $>2 \log_{10}$  above the lower limit of quantification (LLOQ) of the HDV RNA assay.
4. Demonstration of chronicity as evidenced by the presence of HDV RNA in serum for  $\geq 6$  months, or presence of Anti-HDV antibody  $\geq 6$  months.

### ***Exclusion Criteria:***

1. Decompensated liver disease, defined by bilirubin  $>4\text{mg/dL}$ , albumin  $<3.0\text{ gm/dL}$ , prothrombin time  $>2$  sec prolonged, or history of bleeding esophageal varices, ascites or hepatic encephalopathy. Laboratory abnormalities that are not thought to be due to liver disease may not necessarily require exclusion. Patients with ALT levels greater than  $1000\text{ U/L}$  ( $>25$  times ULN) will not be enrolled but may be followed until three determinations are below this level. Patients with an absolute neutrophil count  $<1000/\text{dL}$  and platelets  $<75,000/\text{dL}$  will be excluded from the study as well.
2. Pregnancy, active breast-feeding, or inability to practice adequate contraception, in women of childbearing potential or in partners of such women. Adequate

- contraception is defined as vasectomy in male sexual partners of female participants, tubal ligation in women, or use of two contraceptive methods such as condoms and spermicide combination with an intrauterine device or Depo-Provera, or Norplant.
3. Significant systemic or major illnesses other than liver disease, including, but not limited to, congestive heart failure, renal failure (eGFR <50 ml/min), organ transplantation, serious psychiatric disease or depression (only if felt to be at high risk by the NIH psychiatric consultation service), or active coronary artery disease.
  4. Systemic immunosuppressive therapy within the previous 2 months before enrollment.
  5. Evidence of another form of liver disease in addition to viral hepatitis (for example autoimmune liver disease, primary biliary cirrhosis, primary sclerosing cholangitis, Wilson disease, alcoholic liver disease, ongoing drug induced liver disease, nonalcoholic steatohepatitis (but not steatosis), hemochromatosis, or alpha-1-antitrypsin deficiency).
  6. Active substance abuse, such as alcohol, inhaled or injection drugs within the previous year.
  7. Evidence of hepatocellular carcinoma. This will be determined on the basis of imaging with ultrasound/ CT scan or MRI performed a maximum of 6 months prior to enrollment. Elevated AFP levels will be evaluated clinically and further imaging may be performed if felt necessary.
  8. Evidence of concurrent hepatitis C infection with positive serum HCV RNA.
  9. Any experimental therapy or pegylated interferon therapy within 6 months prior to enrollment.
  10. Active, serious autoimmune disease such as systemic lupus erythematosus, ulcerative colitis, Crohn's disease or rheumatoid arthritis, that is in the opinion of the investigators might be exacerbated by therapy with lambda interferon. This will be evaluated at baseline and during follow-up laboratory testing (including blood and urine studies) in addition to described symptoms at each outpatient visit.
  11. Diagnosis of malignancy in the five years prior to the enrollment with exception granted to superficial dermatologic malignancies.
  12. Evidence of HIV co-infection; HIV 1/2 antibody positivity on serum testing.
  13. Concurrent usage of statins as these drugs inhibits mevalonate synthesis, which reduces protein prenylation.
  14. Concurrent usage of moderate and strong CYP3A inhibitors and inducers.
  15. Concurrent usage of alpha 1 adrenoreceptor antagonist, antiarrhythmic, pimoziide, sildenafil, sedative and hypnotics, ergot and St. John's Wort due to possible effect of ritonavir on hepatic metabolism of these drugs resulting in potentially life-threatening side effects.

16. Clinically significant baseline EKG abnormalities such as QTc interval >450 ms and/or prolonged PR interval.
17. Uncontrolled elevated triglycerides (>500 mg/dL). Patients on lipid lowering therapy other than statins will be eligible for this study.
18. History of pancreatitis from causes other than gallstone pancreatitis. Subjects with a baseline amylase and/or lipase level >3 ULN will be excluded from the study.
19. Inability to understand or sign informed consent.
20. Any other condition, which in the opinion of the investigators would impede the patient's participation or compliance in the study.

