## STUDY PROCEDURES/EVALUATIONS

### Study Procedures

- **Physician Visit** – history and physical, vital signs, review of symptoms, concomitant medications, symptom questionnaire and review of medication compliance while on treatment.
- **History and Physical** –
  - **Full H&P** : A full history and physical examination will be performed at the screening visit as well as inpatient visits.
  - **Interim H&P** : An interim history and physical covering liver and medication related symptoms as well as a limited physical exam will be performed during all other visits.
- **Concomitant medication query** (including dose and indication for each). Documentation of concomitant medication, which may be CYP3A, 2C9, and P-gp substrates, will be performed.
- **Hepatitis B Treatment** To prevent the possibility of a hepatitis B flare during the study, all patients will be treated with nucleos(t)ide analogues while on the study (24 weeks of entecavir or tenofovir + lonafarnib/ritonavir/lambda and 24 weeks of entecavir or tenofovir during the post-therapy monitoring phase). Patients who are not on nucleos(t)ide analogues prior to starting lonafarnib/ritonavir/lambda will be started on either entecavir or tenofovir (which are first-line nucleos(t)ide analogues recommended by the AASLD and EASL for the treatment of HBV) prior to instituting HDV therapy (to reduce the risk of a hepatitis B flare). HBV viral loads will be monitored after starting nucleoside analogue therapy at each outpatient visit during the entire course of study participation. Adequate HBV suppression (serum HBV DNA level <20 IU/mL or undetectable) must be achieved on nucleoside analogue therapy prior to starting HDV therapy which will allow for improved determination of response to experimental HDV therapy. Patients will be informed about the possible adverse effects of these medications during their pretreatment clinic visits and via the package insert that is provided with the medication. Patients will also be offered multiple opportunities to ask questions about these medications during their clinic visits. For patients started on

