d) Highly unlikely risks include the introduction of infection, pain, pneumothorax, arterial puncture, vocal cord paralysis, compression of adjacent structures by a hematoma, pseudoaneurysm formation, cardiac rupture, cardiac tamponade, and death.

4. ***Risk of ionizing radiation:*** The only exposure to radiation in this study is from fluoroscopy which will be utilized during the transjugular liver biopsy and portal pressure measurements. The potential amount of radiation to be received in this study is 2.5 rem that is below the guideline of 5 rem per year allowed for adult research subjects by the NIH Radiation Safety Committee.
5. ***The risks and discomfort of vibration controlled transient elastography (Fibroscan®):*** The Fibroscan® procedure is very similar to a regular ultrasound

examination and both are considered to be procedures with less than minimal risk to patients. Fibroscan® measures how quickly the wave is transmitted through the liver, which gives a measurement of the liver stiffness. The vibration and measurement of liver stiffness is repeated a total of 10 times and takes 5 to 10 minutes to complete. In 5 to 10 percent of persons, the test is not successful. The most common causes for failure include a large amount of fat over the rib cage, or a narrow space between the ribs or fluid in the abdomen.

Although there is minimal risk to patients, rarely, patients may experience mild discomfort between the ribs from having the tip of the probe placed there. This discomfort resolves when the probe is taken off the skin. Fibroscan has been performed on thousands of patients and no adverse effects have been reported.

6. **Magnetic Resonance Imaging Scan (MRI):** MRI scanning may cause anxiety in some patients since current equipment used at the Clinical Center uses a closed tube. Patients will be offered sedatives such as Valium if they express concern about being in a closed space. The MRI will be performed for clinical purposes will be used to screen for hepatocellular carcinoma.

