(Child-Pugh Class B) hepatic impairment. There is no safety data available for severe (Child- Pugh Class C) hepatic impairment patients. Ritonavir is not recommended in patients who have severe hepatic impairment. As we are not going to enroll decompensated liver disease patients, it should not be a problem.

- b. Pancreatitis has been observed in those who developed hypertriglyceridemia. If clinical symptoms or laboratory abnormalities (increased serum amylase or lipase), pancreatitis should be considered. Patients should be evaluated and Ritonavir should be discontinued if a diagnosis of pancreatitis is made.
  - c. Allergic reaction/Hypersensitivity including urticarial, mild skin eruptions, bronchospasm and angioedema have been reported. Cases of anaphylaxis, toxic epidermal necrolysis, Stevens-Johnson syndrome have also been reported. We will discontinue treatment if severe reactions develop.
  - d. Prolong PR interval in some patients. Post-marketing cases of second or third degree atrioventricular block have been reported in patients. The effect on PR interval of co-administrating with other drugs that prolong PR interval (calcium channel blockers, beta blockers, digoxin and atazanavir) has not been studied. But caution should be undertaken when co-administration of Ritonavir with these drugs, especially with those drugs metabolized by CYP3A.
  - e. Metabolism of Ritonavir is mainly through cytochrome P450 CYP3A4. Concurrent usage of other moderate and strong CYP3A inhibitors and inducers will lead to change in plasma concentration of concomitant medications, resulting prolonged therapeutic or adverse effects. Patients who are taking these medications should be excluded.

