### **Adverse Events and Modification of Dose of Prenylation Inhibitor and Ritonavir**

Patients will be monitored for side effects. The use of statins will be prohibited during the course of the study as are the use of moderate and strong CYP3A inhibitor and inducers. Discontinuation of lonafarnib, ritonavir and lambda interferon will be based upon the scoring of adverse events as shown in table 5. The scoring of toxicity will be performed from the CTCAE Version 4.03 with modifications for leukocytes, platelets, prothrombin time, partial thromboplastin time, ALT, AST and bilirubin. These variables have been modified because the National Cancer Institute (NCI) designed the original version with use for cancer trials and not for clinical trials in liver disease. The modified

version to be utilized for this clinical trial accounts for accepted variations of liver tests used in various other liver disease clinical trials by the Liver Diseases Branch. Factors that will lead to discontinuation of lonafarnib, ritonavir and lambda interferon include pregnancy, any grade 3 or any grade 4 adverse events or any adverse event, which, in the opinion of the investigator, places the patient at increased risk. Drug discontinuation may also be based on individual clinical presentations of each subject. For example, AST and ALT values will be evaluated in the context of each individual's baseline values. Rather than utilizing specific cutoff values, which may not be in the best interest of each subject, if the investigator identifies a significant elevation in liver related laboratory tests which may jeopardize the patient's safety, the drug may be discontinued. This is further defined below. If the female becomes pregnant, the patient's obstetrician will be provided with the standard of care guidelines to prevent HBV transmission. Medications will be stopped if pregnancy occurs, with the exception of HBV therapy, given the risk of hepatitis B flare during pregnancy. Lonafarnib, ritonavir and lambda interferon will not be restarted unless another cause for the abnormality or symptom is found.

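### The on-study drug ban restates exclusions 13 and 14 but not exclusion 15, the list the protocol ties to potentially life-threatening ritonavir interactions

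*Combined protocol and SAP*

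**What the plan says.** The Exclusion Criteria contain three items on concurrent drugs. Item 13 covers statins, because they reduce prenylation. Item 14 covers moderate and strong CYP3A inhibitors and inducers. Item 15 covers alpha-1 antagonists, "antiarrhythmic, pimoziide, sildenafil, sedative and hypnotics, ergot" and St. John's Wort. Its stated reason is the "possible effect of ritonavir on hepatic metabolism of these drugs resulting in potentially life-threatening side effects".

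For the treatment period, the section Adverse Events and Modification of Dose of Prenylation Inhibitor and Ritonavir says: "The use of statins will be prohibited during the course of the study as are the use of moderate and strong CYP3A inhibitor and inducers".

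Other text on concomitant drugs:

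- Study Procedures, concomitant medication query: "Documentation of concomitant medication, which may be CYP3A, 2C9, and P-gp substrates, will be performed".
- Hazards and Discomforts, item 11(d), on drugs that prolong the PR interval: "caution should be undertaken when co-administration of Ritonavir with these drugs, especially with those drugs metabolized by CYP3A".
- Hazards and Discomforts, item 11(e), on moderate and strong CYP3A inhibitors and inducers: "Patients who are taking these medications should be excluded".
- Hazards and Discomforts, item 6, on MRI: "Patients will be offered sedatives such as Valium if they express concern about being in a closed space".

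The exclusion-15 list appears once more, in item 18 of the exclusion checklist completed at entry.

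**The concern.** Of the three concurrent-drug exclusions, only item 15 is justified by danger to life, and that danger comes from taking a listed drug while ritonavir is acting. One would expect it to be the first item repeated in the on-treatment rule. Instead the rule repeats the other two.

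A patient who is clear at entry may be given one of these drugs mid-treatment, possibly by an outside physician. Study staff who look up the on-study prohibition will find statins and CYP3A inhibitors and inducers, but not the listed drug, and no instruction to refuse or stop it. The MRI text adds to the uncertainty, since it offers a drug from a class that item 15 excludes without saying whether one-off procedural use is a different matter.

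**Working it through.** There is no figure in the plan to reproduce. The check is a comparison of texts.

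**1. Where each exclusion is named**

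| Exclusion | Entry criteria | Entry checklist | On-study ban (adverse events section) | Ritonavir risks, item 11(e) |
|---|---|---|---|---|
| 13, statins | yes | yes | yes | no |
| 14, CYP3A inhibitors and inducers | yes | not named | yes | yes |
| 15, seven entries | yes | yes | **no** | **no** |

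Two of three are carried into the on-study ban. None of the seven entries of item 15 is named there.

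**2. When the hazard can arise.** Study ritonavir starts after the baseline evaluation and runs at 100 mg twice daily for 24 weeks (Initiation of Treatment; Study Procedures and Schedule). Nobody takes it at entry. An entry screen therefore cannot by itself control a listed drug started later.

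**3. Whether the ban on inhibitors and inducers already covers the list.** That ban concerns drugs that change enzyme activity. By its stated reason, item 15 lists drugs whose metabolism ritonavir changes, so the two groups are not the same. If St. John's Wort is classed as a moderate or strong inducer, which is an assumption because the documents do not classify it, one entry is covered and 7 − 1 = 6 remain. The documents do not say whether individual drugs in the other classes count as inhibitors or inducers.

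**4. What happens at a visit.** Medication review and EKG fall at weeks 1, 2 and 3, at weeks 4, 8, 12, 16 and 20, and at week 24: 3 + 5 + 1 = 9 visits. The instruction at these visits is to record the drug. Item 11(d) adds caution for PR-prolonging drugs. Neither names the item-15 list or gives an action. The checklist does name it, but asks about drugs that alter ritonavir's metabolism. That is the reverse of the reason given in item 15, so the form does not convey why the list matters after dosing begins.

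**5. Procedural sedation.** Table 1 schedules MRI three times.

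- Baseline: before the first dose.
- Week 24: at the visit where ritonavir stops. The order given is "After 24 weeks, therapy will be stopped and patients will again undergo repeated testing including blood draws, imaging, and safety consults".
- Week 48: 48 − 24 = 24 weeks after ritonavir stops.

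Unscheduled visits may include further imaging. Midazolam is described as the usual sedative for percutaneous biopsy. Table 1 puts both scheduled biopsies off ritonavir, at baseline and week 48, but the work-up after Table 4 asks for a biopsy, where feasible, after a treatment-related liver event. None of these places says how sedation relates to ritonavir.

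**The case against.** The strongest reply is that item 15 already reaches the dosing period. It speaks of concurrent use and gives ritonavir as the reason, and no patient takes study ritonavir at entry, so the natural reading is that the drugs are barred while ritonavir is given. On that view the rule is stated once rather than twice. This has force, and it is why a reader should not infer that the protocol permits these drugs on treatment; no sentence does. It does not close the gap. Items 13 and 14 use the same wording and were still restated for the study period, so the omission of item 15 leaves its status in doubt. Even on the generous reading, no action is given when a listed drug is found or requested.

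There are also safeguards. EKG at every scheduled on-treatment outpatient visit bears on rhythm-active drugs, though not on sedation. Each concomitant drug is recorded with dose and indication. The investigator may stop study drug for any event that raises the patient's risk. The branch reviews data weekly and an outside monitor every two weeks. These reduce the risk, but none is a ban.

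On sedation, a reader might infer that the protocol directs staff to give Valium together with ritonavir. The documents do not show that. The baseline scan precedes dosing, the week-24 scan follows the stop of therapy, and the size and duration of any residual effect are not given. A single procedural dose may not have been meant as concurrent use at all. For liver-event biopsies, the adverse events section lists any grade 3 or 4 event as a factor leading to discontinuation of all three drugs, so many such biopsies would be done off ritonavir. The precis and the HVPG risk text place a repeat biopsy or pressure measurement at end of therapy, against Table 1, but that is a separate inconsistency.

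**Conclusion.** The concern holds as a patient-safety consistency gap. The on-study prohibition covers two of the three concurrent-drug exclusions and omits the one tied to potentially life-threatening ritonavir interactions. Six of that list's seven entries are left without a named on-treatment rule if St. John's Wort is assumed to be covered as an inducer, and seven if it is not. The sedation wording is a secondary point: an unresolved exemption, not demonstrated co-dosing.

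The risk cannot be quantified from the documents, which do not say how often the listed drugs would be used. Patient-weeks or doses of ritonavir might be offered as a measure, but they count exposure to ritonavir, not to the interaction. Nor does the gap touch endpoints, sample size or analysis. The absence is established only for the text available; consent pages were removed and may carry drug instructions for patients.

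**What to change.** In the section on adverse events and dose modification, extend the prohibition to every drug and class in exclusion 15 for the whole ritonavir dosing period. State the action if one is found or requested: refuse or stop it, or interrupt ritonavir.

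As a secondary edit, say in the MRI text whether the sedative offer is exempt or restricted when ritonavir is being taken or has just been stopped, which concerns the week-24 scan and any unscheduled one. Apply the same rule to midazolam for any liver-event biopsy done on treatment.

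The cost is a few lines of wording, with no added visits, tests or patients. The downside is that a few patients lose access to some concomitant drugs during dosing or need non-drug measures for MRI.

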## STUDY PROCEDURES/EVALUATIONS

### Study Procedures

- **Physician Visit** – history and physical, vital signs, review of symptoms, concomitant medications, symptom questionnaire and review of medication compliance while on treatment.
- **History and Physical** –
  - **Full H&P** : A full history and physical examination will be performed at the screening visit as well as inpatient visits.
  - **Interim H&P** : An interim history and physical covering liver and medication related symptoms as well as a limited physical exam will be performed during all other visits.
- **Concomitant medication query** (including dose and indication for each). Documentation of concomitant medication, which may be CYP3A, 2C9, and P-gp substrates, will be performed.
- **Hepatitis B Treatment** To prevent the possibility of a hepatitis B flare during the study, all patients will be treated with nucleos(t)ide analogues while on the study (24 weeks of entecavir or tenofovir + lonafarnib/ritonavir/lambda and 24 weeks of entecavir or tenofovir during the post-therapy monitoring phase). Patients who are not on nucleos(t)ide analogues prior to starting lonafarnib/ritonavir/lambda will be started on either entecavir or tenofovir (which are first-line nucleos(t)ide analogues recommended by the AASLD and EASL for the treatment of HBV) prior to instituting HDV therapy (to reduce the risk of a hepatitis B flare). HBV viral loads will be monitored after starting nucleoside analogue therapy at each outpatient visit during the entire course of study participation. Adequate HBV suppression (serum HBV DNA level <20 IU/mL or undetectable) must be achieved on nucleoside analogue therapy prior to starting HDV therapy which will allow for improved determination of response to experimental HDV therapy. Patients will be informed about the possible adverse effects of these medications during their pretreatment clinic visits and via the package insert that is provided with the medication. Patients will also be offered multiple opportunities to ask questions about these medications during their clinic visits. For patients started on

nucleos(t)ide analogue therapy as a result of their participation in this protocol, the medication will be administered under this protocol after the consent has been signed and eligibility is determined. If the patient has been taking a nucleos(t)ide analogue prior to enrolling in this study, the specific nucleos(t)ide(s) analogue will be continued. The currently approved nucleoside analogues for hepatitis B include: lamivudine, adefovir, tenofovir, entecavir and telbivudine. At the conclusion of participation in this study, subjects that were prescribed nucleoside analogue therapy by their outside practitioners will be continued on therapy (if clinically indicated) and they will receive this therapy from their outside physicians. For subjects that are started on nucleoside analogue therapies for the purposes of participation in this study, nucleoside analogue therapy may be continued after completion of this study if clinically indicated. If this is the case, therapy will be continued under the 91-DK-0214 protocol, with encouragement that therapy should be received from their outside physicians. Otherwise, if not clinically indicated, nucleoside therapy will be discontinued at the conclusion of participation in this study.

- **Symptom Questionnaire** provides information on categorical presence of symptoms as well as their severity, pattern and frequency (Appendix 1)
- **EKG** – Patients will undergo electrocardiogram (EKG) evaluations collected in digital format due to the rare instances of asymptomatic bradycardia, PR prolongation and QT/QTc interval prolongation described in oncologic trials with use of lonafarnib.
- **Imaging**
  - **Ultrasound and Fibroscan** - An abdominal ultrasound with sheer wave elastography and vibration controlled transient elastography (Fibroscan ®) will be performed for clinical staging of liver disease and to evaluate for hepatocellular carcinoma, masses or any other findings that may preclude a safe transjugular liver biopsy with hepatic venous pressure gradient measurements.
  - **MRI** A structural examination of the liver will be performed via magnetic resonance imaging with gadolinium. An MRI without contrast will be performed in the event that contrast cannot be administered.
- **Liver Biopsy with Hepatic Venous Pressure Gradient (HVPG) Measurements**
  - **Transjugular Liver Biopsy with HVPG** : A transjugular liver biopsy will be performed in the interventional radiology suite with measurement of hepatic venous pressure gradient. If size of core during one pass permits, a small piece of liver will be flash frozen at -80 C for further analysis.
  - **Percutaneous Liver Biopsy** – in the event that the transjugular liver biopsy cannot be performed (ie: technical difficulty), a percutaneous liver biopsy will be performed.

- **Consults**
  - **Reproductive** - A reproductive endocrinology or urological consultation for evaluation of current and future reproductive potential, the potential of reversibility in the event that reproductive toxicity occurs, and guidance on potential contraceptive methods will be obtained. Sperm samples will be obtained, wherever possible, based on the recommendations of the consult. Sperm sampling will be offered and if obtained, given that the normal spermatogenesis cycle is 90 days, a repeat sperm sample will be evaluated at 90 days after therapy has been completed. Patients will also be provided the opportunity to store sperm or eggs at an outside facility of their own choosing and at their own cost prior to starting therapy.
  - **Ophthalmologic** – an ophthalmologic evaluation including vision testing as well as retinal exams will be performed.
- **Medication Compliance Assessment** Compliance with drug dosing will be monitored through patient diaries and pill counts at outpatient visits. Patients will be asked to complete drug diaries as they take their study medication including the date and time. They will be asked to bring unused medication with them and the residual pills will be counted and retained. If compliance falls below 90%, the patient will be counseled about the importance of complying with drug therapy and made aware that if compliance falls below 80% their participation in the study may end. If compliance falls below 80%, the patient may be withdrawn from the study. Reasons for non-compliance will be assessed and documented in the patients record.

